### **Rationale for Version 3.0**

[figure not shown]
The changes from Version 2.0 to Version 3.0 of the Statistical Analysis Plan were motivated by additional protocol amendments subsequent to the finalization of Version 1 of the SAP. Version 2 was finalized 24 Sept 2015 under protocol Version 5, which included larger expansion cohorts which would be the focus of efficacy analyses. The protocol has been amended two times since Version 2 of the SAP (Protocol Version 6, 01 Jun 2016, and Protocol Version 7, 26 Jan 2017). Additional modifications were made to provide clarity to the statistical methods used in the planned analysis.

In general, the notable modifications include:

- Clarification of a modified Intent-to-Treat subset of patients to exclude patients without sufficient treatment or who have no post-baseline data for the primary endpoint, patients who did not have at least 28 doses of study treatment, or who had a heart or lung transplant over the course of the 16 week study
- Clarify that the primary object of this study is to identify appropriate doses to be used for further study, and that this will be done through assessing the totality of data rather than a single endpoint
- Provide more guidance associated with the methods used in the primary efficacy analysis
- Specify the pooling strategy for the primary analysis
- Specify additional subgroup analyses of 6MWD
- Updated visit windows for unscheduled and end of treatment visits
- Added visit windows for unscheduled and end of treatment visits in Part 2
- Updated appendices to only include information not found in external documentation
- Added specifications for calculating estimated glomerular filtration rate (eGFR)

[figure not shown]
## 1. INTRODUCTION

This two-part trial will study the safety, tolerability, and efficacy of bardoxolone methyl in patients with pulmonary hypertension (PH). Part 1 will be a double-blind, randomized, dose-ranging, placebo-controlled treatment period and Part 2 will be an extension period. Part 1 and Part 2 may be repeated for additional cohorts at the discretion of Reata.

The study includes an initial dose-ranging phase followed by a dose-titration phase. Within the dose-ranging phase, the effects of bardoxolone methyl in two cohorts of WHO Group I PAH (cohort 1: baseline 6MWD  $\leq$  450 m; cohort 2: baseline 6MWD  $>$  450 m) will be explored to identify an appropriate dose range to be used in the dose-titration phase. Each sequential dose group enrolled in the dose-ranging phase will include 8 patients randomized 3:1 (bardoxolone methyl:placebo).

Within the dose-titration phase, the effects of titration dosing bardoxolone methyl in WHO Group I PAH (Cohort 3 with 2 sub-cohorts: (1) 3a: CTD-PAH; (2) 3b: non-CTD-PAH) as well as subsets of WHO Group III/V PH (Cohort 4 with four sub-cohorts: (1) 4a: CTD-ILD; (2) 4b: IPF; (3) 4c: NSIP/IIP; (4) 4d: Sarcoidosis). Each sub-cohort in the dose-titration phase is expected to enroll up to a maximum of 72 patients, randomized 2:1 (bardoxolone methyl:placebo).

This version of the SAP describes the analyses planned throughout the course of this study. Some analyses may be performed prior to database lock. Any substantive changes made to the statistical analysis plan after any formal interim reviews will be clearly documented and a justification will be given in the CSR.

This SAP is based on Version 7 of the study protocol dated January 26, 2017. If the protocol is subsequently amended, this SAP may be amended as well. Should the SAP and the protocol be inconsistent with respect to the planned analyses, the language of the SAP is governing. All analyses will be conducted using SAS version 9.2 or higher.

## 1.5 Study Objectives

The objectives of the study are as follows:

### 1.5.2 Primary Objectives

The primary objective of this study is to determine the recommended dose range for further study of bardoxolone methyl.

Rather than specifying a single rule, clinical judgement and totality of information from the analyses described below will be used to recommend a dose range for further study. Clinical judgment will be guided by the balance of maximized efficacy within the range of doses viewed as having acceptable safety profiles based on available data. Thus, no single endpoint will be used to assess the primary objective.

### 1.5.3 Secondary Objectives

The secondary objectives of this study are:

- To assess the change from baseline in 6-minute walk distance (6MWD) in those patients treated with bardoxolone methyl versus patients given placebo for 16 weeks.
- To assess the safety and tolerability of 16 weeks of treatment with bardoxolone methyl versus 16 weeks of administration of placebo.

## 1.6 Endpoints

### 1.6.2 Primary Efficacy Endpoint

The primary efficacy endpoint is an overall change from baseline in 6MWD through Week 16 for bardoxolone methyl compared to placebo.

### 1.6.3 [REDACTED]

[REDACTED]

[REDACTED]

[REDACTED]

[REDACTED]

[REDACTED]

[REDACTED]

[REDACTED]

[REDACTED]

#### 1.6.4 Pharmacokinetic Endpoints

Analysis of PK data will be described in a separate PK analysis plan and presented in a standalone PK report.

#### 1.6.5 Safety Endpoints

The safety endpoints include frequency, intensity, and relationship to study drug of adverse events and serious adverse events, concomitant medications, and change from baseline in the following assessments:

- Physical examinations;
- Vital sign measurements;
- 24-hour ambulatory blood pressure monitoring (ABPM);
- 12-lead electrocardiograms;
- Clinical laboratory measurements;
- Weight.

#### 1.7 Determination of Sample Size

A sample size of 8 patients randomized at a 3:1 (bardoxolone methyl : placebo) assignment ratio in each dose level within cohort includes 6 patients treated with bardoxolone methyl for identification of gross safety signals. A small number of patients at each dose is not expected to fully characterize safety, therefore issues of concern identified in only 1 of 6 patients (16%) treated with bardoxolone methyl may suggest the need to collect additional information before escalating the dose, by either adding more patients at the current dose level or a lower dose as determined by the PSRC. Each additional dose level enrolled at selected doses adds 6 more patients treated with bardoxolone methyl to further characterize safety, tolerability, and efficacy.

[REDACTED]

All eligible patients from Part 1 will be included in Part 2, and no new patients will be randomized to Part 2 of the study.

#### 1.8 Study Cohorts

As described in Section 1, this study includes 2 cohorts in the dose-ranging phase and 6 sub-cohorts (within 2 overarching cohorts) in the dose-titration phase. Analyses described in this SAP may be performed separately by cohort. The Part 1 and Part 2 safety and efficacy analyses will be summarized by randomized treatment, pooling all placebo patients and all active patients into various subgroups:

- All PAH patients (Cohorts 1, 2, 3a, and 3b patients)
- All CTD-PAH patients (CTD-PAH patients in Cohorts 1, 2, and 3a)

- All Non-CTD PAH patients (Non-CTD PAH patients in Cohorts 1, 2, and 3b)
- All PH patients (Cohorts 4a, 4b, 4c, 4d)

In addition to the subgroups listed above, the eGFR, six-minute walk test, and pulmonary function testing results will be summarized by individual cohort.

All patients enrolled in the study will follow the same schedule of assessments, including a placebo-controlled period (Part 1) followed by an extension period (Part 2).

### **1.9 Timing of Analysis**

Analyses of Part 1 and Part 2 may be performed as data accumulate to allow for planning of future studies. Timing of analyses will be determined solely by the Sponsor. As this is an exploratory study, no statistical adjustments will be made for repeating an analysis.

#### **1.9.2 Protocol Safety Review Committee**

A Protocol Safety Review Committee (PSRC) will assess the starting dose and each new dose level of bardoxolone methyl for safety and tolerability based on review of all available data for this study at the time of each review. PSRC reviews will occur after the Week 4 data are available for the first eight patients enrolled at each new dose level combined across both the  $\leq 450$  m and  $> 450$  m cohorts.

#### **1.9.3 Part 1 (placebo-controlled period) Results**

For a particular cohort, the primary analysis of Part 1 will be performed after all patients enrolled in that cohort have completed Part 1.

#### **1.9.4 Part 2 (extension period) Results**

In addition to the final reporting of Part 2 data for each cohort, analysis of Part 2 data will be performed for regulatory interactions as determined by the Sponsor. The final analysis of Part 2 data for a particular cohort will be performed after all enrolled patients complete their last Part 2 visit.

### **1.10 Changes from Protocol**

The primary efficacy endpoint was defined in Version 1 of the protocol as change from baseline in 6MWD at Week 16. The primary objective of this longitudinal phase 2 study is to identify the appropriate dose range for further study of bardoxolone methyl in PAH patients. Each dose level includes 6 active and 2 placebo patients within each cohort. Therefore, to maximize the information attained from each patient in the estimate of treatment effect on an endpoint known to have large variability, the primary efficacy endpoint was modified. The original endpoint as defined in the protocol (i.e., treatment effect at Week 16) will also be estimated, along with estimates at other timepoints. The totality of the results will be considered in dose range selection for future studies.

Quality of life, oxygen use and pulse oximetry were not defined in the protocol as exploratory endpoints. These four endpoints will be analyzed using approaches described later in this SAP.

## **2. STUDY CONDUCT**

### **2.1 Randomization**

Eligible patients in Cohorts 1 and 2 will be assigned a dose cohort type based on baseline 6MWD, as described in the study design section in the protocol. Eligible patients in Cohorts 3 and 4 will be assigned a dose cohort type based on PAH etiology, as described in the study design section in the protocol. Based on the determined cohort, patients will be randomized to bardoaxolone methyl or placebo for Part 1 of the study according to the treatment assignment regimen.

In this double-blind study, all patients, investigators, site personnel, laboratories and central readers with direct involvement in the conduct of the study and their designees will be blinded to treatment assignments. Appropriate measures will be taken to ensure the blind is maintained for the patients and personnel mentioned previously to reduce potential bias. To maintain the blind, investigators will distribute blinded study drug kits to patients as directed by the IWRS system.

Treatment assignments will be managed by an IWRS system. The only people with direct access to treatment assignments will be those individuals who develop and maintain the randomization code, the individuals involved in the implementation and operation of the IWRS system, and the PSRC. Some Sponsor personnel will be unblinded to individual treatment assignments.

Upon starting Part 2 of the study (i.e., the extension phase) all patients will receive bardoaxolone methyl.

### **2.2 Data Monitoring**

Refer to the PSRC plan for details around the timing and conduct of PSRC meetings. The PSRC will be used to evaluate interim analysis results and to determine dose escalation. All summaries/analyses by treatment arm for the PSRC review will be prepared by an Independent Data Coordinating Center (IDCC) [REDACTED]. During the study the PSRC will review, in an unblinded manner, available safety data through at least Week 4 for all patients in each recently opened cohort and available data from prior cohorts in order to determine if escalation to the next highest dose is warranted.

### **2.3 Data Sources**

Refer to the data management plan for Electronic Case Report Form (eCRF) data specifications and the non-eCRF guidelines for details around data sources external to the eCRF. All data collected in the eCRF and external data sources will be presented in by-patient data listings.

### 3. STATISTICAL METHODS

The analyses outlined in this SAP will supersede those specified in the protocol for the purpose of a regulatory filing.

Screen failure patients will be summarized by reason for screen failure. Screen failure patients will not be included in any other analyses described in this document. Statistical methods in study Part 1 (Section 3.4) and study Part 2 (Section 3.5) are described separately.

All analyses will be presented by cohort. There are no pre-planned analyses to combine same dose levels across multiple cohorts. Titration cohorts (cohort 3 and cohort 4) will not examine individual dose levels. Summaries of titration cohorts will be grouped according to the randomized treatment: bardoxolone methyl or placebo.

#### 3.1 Analysis Populations

Populations for primary analyses of efficacy and safety from Part 1 of the study are described below. Based on results of the primary analyses, additional populations for sensitivity analyses may be performed as post-hoc analyses.

##### 3.1.2 Intent-to-treat (ITT) Population

The ITT population includes all randomized patients. The ITT analysis will be done by randomized treatment, pooling all placebo patients within each cohort. No data will be imputed for ITT analyses. The ITT population will be used for analyses of exploratory endpoints except 6MWD. The ITT analysis will be summarized by randomized treatment, pooling all placebo patients and all active patients into various subgroups:

- All PAH patients (Cohorts 1, 2, 3a, and 3b patients)
- All CTD-PAH patients (CTD-PAH patients in Cohorts 1, 2, and 3a)
- All Non-CTD PAH patients (Non-CTD PAH patients in Cohorts 1, 2, and 3b)
- All PH patients (Cohorts 4a, 4b, 4c, 4d)

In addition to the subgroups listed above, the eGFR and pulmonary function testing results will be summarized by individual cohort.

All 6MWD analyses will use the mITT population.

##### 3.1.3 Modified Intent-to-treat (mITT) Population

The purpose of this Phase 2 study is to estimate the treatment effect of bardoxolone methyl on 6MWD in patients with PAH, and to identify an appropriate dose for further development. Estimated treatment effect from this study will be used to power future trials of bardoxolone methyl in PAH patients.

The mITT population will include all randomized patients who received at least 28 doses of study treatment, did not undergo heart or lung transplantation during the treatment period, and performed at least one post-baseline 6MWT assessment. The primary population for efficacy analyses of the primary endpoint will be the mITT population. The mITT analysis will be done by randomized treatment, pooling all placebo patients and all active treatment patients.

Since treatment effect is expected to be observed within the first few weeks of treatment and sustained over time, missing data will be imputed using last observation carried forward (LOCF) for mITT analyses. Missing data will only be imputed for the 6MWD analysis.

#### **3.1.4 Safety Population**

The safety population includes all randomized patients who were dispensed any dose of study drug during the study treatment period. Patients who received one or more doses of bardoxolone methyl will be assigned to the corresponding bardoxolone methyl treatment arm even if it was given in error. If a patient is dispensed bardoxolone methyl at more than one dose, the patient will be included in the safety population at the highest dose dispensed. All safety data will be analyzed for the safety population according to the medication actually dispensed.

### 3.2 Analysis of Study Conduct

Study enrollment, study treatment exposure and compliance, reasons for study termination will be summarized by treatment arm for all randomized patients within each cohort. Major protocol deviations, including violations of inclusion/exclusion criteria, based on information captured in the eCRFs will be reported and summarized by treatment arm. Any inclusion/exclusion violations will be listed separately, and will only be summarized if it is considered a major protocol deviation.

### 3.3 Analysis of Treatment Group Comparability

Demographic information (age, sex, ethnicity, race), baseline characteristics (baseline BMI, weight) and baseline disease characteristics (including PAH classification and details, time since diagnosis, baseline PAH concomitant medications, thromboembolic disease assessment, pulmonary function testing, oxygen use during 6MWTs and available baseline right heart catheterization data) will be summarized by treatment arm for all randomized patients.

Descriptive baseline summaries of continuous data will present the group mean, standard deviation, median, minima, and maxima. Descriptive summaries of discrete data will present the category counts as frequencies and percentages.

Unless otherwise stated, the baseline value of any variable will be defined as the last available value recorded prior to the first administration of bardoxolone methyl/placebo. Missing values will not be imputed, unless otherwise noted, and will be tabulated as missing.

### 3.4 Analysis of Part 1

Part 1 data will be analyzed using the analysis populations defined in [Section 3.1](#). Separate analyses will be performed by each cohort. Part 1 analyses will only include data from the placebo controlled portion of the study. If a subject does not complete Part 1, or chooses not to enter Part 2, then all their data will be used in Part 1. If a subject enters Part 2, then all data up to and including the Week 16 visit will be included in Part 1.

#### 3.4.2 Exposure of Study Medication and Patient Adherence

Patient disposition, study treatment exposure, and compliance will be summarized for each treatment arm with descriptive statistics.

The overall exposure (days) is calculated as [(Week 16 visit date) – (date of first dose) + 1].

If a subject discontinues treatment prior to Week 16, the date of last dose will be used for calculating overall exposure.

Each study drug kit contains 4 bottles (Bottle A, B, C, D). Each bottle contains 30 capsules at the time of dispensing, and the number of capsules remaining in each bottle is recorded in the drug return CRF. Administered doses will be estimated for each bottle based on the number of capsules dispensed minus the number returned. The compliance is calculated for each bottle (bottle 'X') as: 
$$\frac{[(\text{Total number of kits dispensed in Part 1}) \times 30] - (\text{Total Bottle 'X' capsules returned})}{(\text{Study part exposure days})}$$

For the disposition summary, a patient who completes part 1 is defined as any patient who completes the Week 16 visit while taking study treatment (i.e., end-of-treatment page is blank or date of last dose is within 2 weeks before Week 16 visit date).

### 3.4.3 Concomitant Medications

The WHO Drug Dictionary will be used to classify all medications recorded during this study. Medications taken from 28 days prior to the administration of the first dose of bardoxolone methyl/placebo through the final follow-up visit will be recorded in the concomitant medication forms. The numbers and percentages of patients who had taken any baseline concomitant medications (i.e., start date on or before study Day 1 and stop date after Day 1) will be summarized by medication for each treatment arm. The numbers and percentages of patients who had started taking any post-baseline concomitant medications during Part 1 (i.e., start date after study Day 1 through Week 16) will be summarized by medication for each treatment arm. Study medications with start date after Week 16 will be excluded from the Part 1 summaries of concomitant medications, unless the patient did not continue into Part 2.

In the presence of partial dates, the available data (month and/or year) will be compared to the appropriate study reference dates to identify the most likely study period.

### 3.4.4 Efficacy Analysis

Analysis of the 6MWD will be performed using the mITT analysis set on all available data. Missing 6MWD data in Part 1 will be imputed using LOCF as described in Section 3.1.2. No imputation will be performed for missing 6MWD data in Part 2.

The CRF nominal study visits (i.e., Week 4, Week 8, Week 12, and Week 16) will be used for all 6MWT efficacy analyses. For subjects that prematurely discontinue treatment before Week 16 with a 6MWT recorded at the End of Treatment (EOT) assessment, that EOT 6MWD will be used in analysis for the nominal protocol visit most closely matching the subject's visit schedule. For all other efficacy analyses, the value closest to the target study day should be used (Section 3.7.2). In Part 1, LOCF will be applied to impute missing 6MWD values after analysis values are obtained taking into consideration the End of Treatment assessment, if applicable. For all other efficacy variables besides 6MWD, LOCF should not be used, and no imputation for missing data should be performed.

Analysis will pool all active doses within cohort for comparison with placebo in Part 1.

The analyses will be repeated for subgroups defined by PAH etiology in Part 1 (i.e., connective tissue disease vs non-connective tissue disease).

Given the exploratory nature of this study, sensitivity analysis may be performed in an ad hoc manner.

Plots will be generated to summarize 6MWT results by randomized treatment, pooling all placebo patients and all active patients into various subgroups:

- All PAH patients (Cohorts 1, 2, 3a, and 3b patients)
- All CTD-PAH patients (CTD-PAH patients in Cohorts 1, 2, and 3a)
- All Non-CTD PAH patients (Non-CTD PAH patients in Cohorts 1, 2, and 3b)
- All PH patients (Cohorts 4a, 4b, 4c, 4d)

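### The SAP does not say which 6MWD estimate in PAH patients is primary, the cohort-level or the pooled one, and its pooled model has no cohort term

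*SAP*

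**What the plan says.** The SAP's change summary lists this among the purposes of Version 3.0: "Specify the pooling strategy for the primary analysis". The body then gives three kinds of instruction.

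- **Cohort level.** Section 3.4.4: "Analysis will pool all active doses within cohort for comparison with placebo in Part 1". Section 3: "All analyses will be presented by cohort. There are no pre-planned analyses to combine same dose levels across multiple cohorts". Section 3.4 (Analysis of Part 1): "Separate analyses will be performed by each cohort". Section 1.9.3 attaches the word primary to this level: "For a particular cohort, the primary analysis of Part 1 will be performed after all patients enrolled in that cohort have completed Part 1".
- **All patients pooled.** Section 3.1.3 makes the mITT population primary for the primary endpoint, and continues: "The mITT analysis will be done by randomized treatment, pooling all placebo patients and all active treatment patients". The ITT paragraph (3.1.2) limits its pooling of placebo patients to each cohort. The mITT paragraph carries no such limit.
- **Pooled groups.** Section 1.8 has Part 1 efficacy summarised by randomised treatment, "pooling all placebo patients and all active patients into various subgroups": All PAH, CTD-PAH, non-CTD PAH, and the Cohort 4 PH patients. It makes by-cohort analysis optional in one sentence, then adds walk-test summaries by individual cohort.

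Section 3.4.4.1 directs the estimate at PAH patients and names no cohort. Its example model contains treatment, week and their interaction only. Section 3.1.3 says the estimated effect will be used to power later trials in PAH patients.

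**The concern.** A programmer given section 3.4.4.1 cannot tell which dataset feeds the primary model: one run per PAH cohort, one All-PAH run, or both with one of them called primary. If the label is settled after results are seen, the estimate carried into the next trial's sample size can be the most favourable of several. An effect chosen for its size leads to an underpowered trial.

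There is also a modelling issue. Cohorts 1 and 2 are randomised 3:1, and each subcohort of Cohorts 3 and 4 is randomised independently at 2:1. If these are pooled without a cohort term, some of the difference in mean change between cohorts enters the treatment effect.

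**Working it through.** **1. Sizes (protocol 7.2).** Planned: 38 + 16 + 6 × 24 = 198. Maximum: 38 + 16 + 6 × 72 = 486. Both match the stated totals. The PAH part at planned size is 38 + 16 + 24 + 24 = 102 patients.

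**2. Arms implied by the allocation ratios.** Cohort 1 is 28.5 active to 9.5 placebo, Cohort 2 is 12:4, and 3a and 3b are 16:8 each. All PAH is therefore 72.5:29.5.

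**3. Does the level matter?** The 95% half-width is 1.96 × SD × √(1/n_active + 1/n_placebo). The visible text gives no SD, so I assume 40, 55 and 70 m for the patient-level mean change.

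| Estimate | SD 40 | SD 55 | SD 70 |
|---|---|---|---|
| Cohort 1 | 29.4 m | 40.4 m | 51.4 m |
| Cohort 2 | 45.3 m | 62.2 m | 79.2 m |
| 3a or 3b (24 each) | 33.9 m | 46.7 m | 59.4 m |
| All PAH | 17.1 m | 23.5 m | 30.0 m |

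With 72 in each of 3a and 3b and SD 55 m, the half-width is 26.9 m for 3a or 3b and 16.6 m for All PAH.

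**4. Picking among the four PAH cohorts with no true effect.** The cohorts are independent.

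- Chance that at least one 95% interval lies wholly above zero: 1 − 0.975⁴ = 9.6%, against 2.5% for one named estimate. This does not depend on the SD.
- Average of the largest estimate: the expected maximum of four independent standard normals is about 1.03. Treating each cohort as about 24 patients at 2:1, SE = SD × √(1/16 + 1/8) = 0.433 × SD.
  - SD 40: 1.03 × 17.3 = 17.8 m
  - SD 55: 1.03 × 23.8 = 24.5 m
  - SD 70: 1.03 × 30.3 = 31.2 m

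**5. Adding the pooled PAH groups.** All PAH, CTD-PAH and non-CTD PAH overlap with the cohorts, so this was simulated: seven candidates, 40,000 runs, and an assumed CTD share of 25 to 50% in Cohorts 1 and 2. At least one interval lay wholly above zero in about 12% of runs. The candidate with the largest standardised effect averaged about +25 m at SD 55 m (18 to 32 m over SD 40 to 70 m). With 72 per subcohort it averaged about +20 m (14 to 25 m).

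**6. No cohort term.** Cohorts 1 and 2 supply 40.5/72.5 = 55.9% of All-PAH active patients but 13.5/29.5 = 45.8% of placebo patients. The unadjusted shift is (0.559 − 0.458) × the difference in mean change between dose-ranging and titration cohorts, about 1.0 m per 10 m. At 72 per subcohort the shares are 40.5/136.5 = 29.7% and 13.5/61.5 = 22.0%, giving about 0.8 m per 10 m.

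**The case against.** The best defence is that the SAP does choose a level. Four sections point to the cohort, and one of them, 1.9.3, schedules a primary analysis for each. The protocol synopsis also separates the cohorts so that each can be assessed independently. On this reading, section 3.1.3 means pooling over doses, section 3.4.4 likewise mainly settles how doses are combined, its four pooled groups are for plots, and section 1.8 only adds further summaries. Both levels would be visible in the report. The study is described as exploratory, and section 1.5.2 says no single endpoint decides the dose range.

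Much of this stands. Reporting two levels is not an error, no confirmatory test is visible, and the consequence is limited to how the effect size is read and reused. It does not settle the point, because the mITT paragraph that fixes the primary population lacks the within-cohort limit written for ITT, section 1.8 makes by-cohort analysis optional, and section 3.4.4.1 addresses PAH patients as a whole. Text after the primary model and in the sample-size section is blacked out, so a clarification may exist there. The visible sentences would still need to agree.

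A reader might go further in two ways that the documents do not support. One is to count all eight cohorts and an all-patient pool as candidates, giving 1 − 0.975⁸ = 18%. Sections 3.1.3 and 3.4.4.1 concern PAH, section 1.8 keeps the PH group apart, and no sentence names a combined PAH and PH group. The other is to infer that unblinded sponsor staff will select the result. Section 1.9 gives timing to the sponsor and section 2.1 says some sponsor personnel are unblinded. Neither says these are the same people, or that they choose the primary estimate.

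**Conclusion.** The visible SAP leaves the primary 6MWD estimate in PAH patients unranked between the cohort and pooled levels. That creates an opportunity for choice after the fact; it does not show that a choice was made, and no error-rate claim is broken. Choosing the best result would raise the chance of an apparently favourable interval from 2.5% to about 10% (four cohorts) or 12% (with the pooled PAH groups). The largest cohort estimate would average roughly +18 to +31 m with no true effect. The metre figures rest on the assumed SD range and on about 24 patients per cohort. Cohorts 1 and 2 differ from that size, and larger subcohorts reduce the figures. The missing cohort term is a separate and small defect, about 1 m per 10 m, set against an All-PAH half-width of 17 to 30 m at planned size. The point should be corrected, but it does not undermine the dose-ranging objective.

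**What to change.** - In section 3.4.4, name one primary level before further unblinded results are reviewed, and label the other supportive. All PAH (Cohorts 1, 2, 3a and 3b) matches the target in 3.4.4.1. Each PAH cohort separately would also be acceptable, provided the four have equal standing.
- Include cohort or subcohort as a fixed factor in every model that pools across cohorts.
- Analyse Cohort 4 separately, with subcohort as a factor when its subcohorts are pooled.
- Reconcile sections 1.8, 1.9.3, 3, 3.1.3, 3.4 and 3.4.4. Section 1.9.3 must be included because it ties the timing of the primary analysis to each cohort.

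The cost is SAP wording and one model term; no new data are needed. If All PAH is chosen, the primary analysis has to wait until every PAH cohort has completed Part 1.
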